- requires or prolongs hospital stay
- results in persistent or significant disability or incapacity
- a congenital anomaly or birth defect
- an important medical event

Important medical events are those that may not be immediately life threatening, but based upon appropriate medical judgment may jeopardize the subject, and may require intervention to prevent one of the other serious outcomes noted above. For example, drug overdose or abuse, a seizure that did not result in in-patient hospitalization, or intensive treatment of bronchospasm in an emergency department would typically be considered serious. All adverse events that do not meet any of the criteria for serious will be regarded as **non-serious adverse events**.

Collection and Recording of AEs and SAEs.

Adverse Events and SAEs will be collected by spontaneous self-report.

Research staff are trained to inquire (time of onset, nature of issue reported, possible relation to study, review of previously reported side effects or concerns, concomitant medications, severity/intensity, etc.) about any notable side effects or medical concern reported by participants. Side effects will be rated by participants utilizing the following severity scale: 0 (None=No Concerns), 1 (Mild=Side Effect or event does not interfere with usual daily activities), 2 (Moderate= Side effect does interfere with some activities), and 3 (Severe=No normal activities are possible). Any severe (or a pattern of modern) side effects or notable medical concerns will be reported to the Project Manager, Study Physician, and Principal Investigator to determine a course of action and relationship (causality) to the study procedures. This

consultation, including all relevant information will be documented via email. The clinical course of each event will be followed until resolution, stabilization, or until it has been determined that the study treatment or participation is not the cause.

Information surrounding AEs and SAEs are recorded and secured within the appropriate source documents (i.e. subject chart), Case Report Forms (e.g. SEC form, etc.) when applicable, an AE note or SAE report, and the AE/SAE log within the Study Administrative File.

Documentation of AEs will include the following information:

- Protocol name
- Subject identifier
- Description of the event
- Date and time of onset and outcome
- Intensity/Severity
- Action taken
- Relationship (causality) to the study
- Outcome

Documentation of SAEs will include the following information:

- Protocol name
- Subject identifier
- Description of the event
- Date and time of onset
- Current status
- The reason why the event is classified as serious
- Action taken
- Investigator assessment of the association between the event and study treatment
- Welfare of subjects/Outcome
- Follow-Up Plan (if applicable)

Management of SAEs or Other Study Risks.

The Study Physician will oversee the management of all SAEs and other study risks. SAEs will be monitored closely until the event has been stabilized and/or the subject has been referred to the care of their primary care physician. The Study Physician will also review data collected during the medical history portion of the Intake Visit for all subjects who experience a SAE and, when required, will provide follow-up consultation with the participant. All instances of consultation will be recorded.

AE, SAE, and Unanticipated Problems Reporting.

The procedures for unanticipated problem, adverse event, and serious adverse event reporting are consistent with NIH and UPenn-specific guidelines and are as follows:

1. Alert the IRB of any and all reports of unanticipated problems involving risk to subjects or others, AEs, and SAEs when appropriate (i.e. within 10 business days, summary at continuing review, etc.). AEs and SAEs meeting reportable event/unanticipated problem guidelines (unexpected and related) will be submitted to the appropriate IRB within 10 business days of occurrence using the on-line system. If an AE/SAE involved a death and indicates that participants and others are at an increased risk of harm, the event will be reported to the IRB within 3 days.
2. Inform applicable members of the study team of any and all reports of adverse events.

In addition to unanticipated problems (including applicable AEs and SAEs), the following events will be promptly reported to the IRB within 10 business days:

1. Any adverse experience that, even without detailed analysis, represents a serious unexpected adverse event that is rare in the absence of drug exposure (such as agranulocytosis, hepatic necrosis, Stevens-Johnson syndrome).
2. Any adverse event that would modify the protocol or informed consent form, or would prompt other action by the IRB to assure protection of human subjects.
3. Information that indicates a change to the risks or potential benefits of the research, in terms of severity or frequency. For example:
 - An interim analysis indicates that subjects have a lower rate of response to treatment than initially expected.
 - Safety monitoring indicates that a particular side effect is more severe, or more frequent than initially expected.
 - A paper is published from another study that shows that an arm of your research study is of no therapeutic value.
4. Change in FDA safety labeling or withdrawal from marketing of a drug, device, or biologic used in a research protocol.
5. Breach of confidentiality.
6. Change to the protocol taken without prior IRB review to eliminate apparent immediate hazard to a research subject.
7. Incarceration of a subject when the research was not previously approved under Subpart C and the investigator believes it is in the best interest of the subject to remain on the study.
8. Complaint of a subject when the complaint indicates unexpected risks or the complaint cannot be resolved by the research team.
9. Protocol violation (meaning an accidental or unintentional deviation from the IRB approved protocol) that in the opinion of the investigator placed one or more subjects at increased risk, or affects the rights or welfare of subjects.

5. Management of Information for Multi-center Research where a Penn Investigator is the Lead Investigator of a multi- center study, or Penn is the lead site in a multi-site study.
Not applicable.

6. Risk/Benefit Assessment

Research staff will monitor subjects closely during their participation. Thus, the risk to benefit ratio for this project is perceived to be low and justifies its implementation.

SUBJECT COMPENSATION

Participants will be compensated for the time and effort required to complete study procedures. Participants will be given the means to travel to and from their appointments at no cost to them. Participants will be given two options for travel coverage: 1) participants may elect to receive a flat rate of \$10/day to cover their travel expenses to and from the center or 2) participants may elect to use a round-trip ride service (i.e. Lyft.) which will be arranged and paid for in full by the research study. If participants choose to use the ride service, they will not receive \$10 for their travel reimbursement.

Participants will be eligible for compensation only if they complete the visits/assessments listed below (Table 3). Participants who are found ineligible for any reason during Study Visits will only be provided \$10 for their time, in addition to their preferred travel coverage for that session. Participants who withdraw partway through a session (other than the Intake session) may receive prorated compensation for that session. Through participation in this research study participants are estimated to earn up to \$810 in visit compensation. If the participant elects to use the ride service, all travel will be paid for by the research study. If the participant elects to travel to and from their appointments independently, they will be reimbursed \$10/visit (\$120 over the course of the study) to put towards their travel expenses.

Recruitment and Retention Pilot: Upon completion of all requirements for a given visit, participants randomized to CM will receive 5 lottery jar draws for that visit. Attendance at all visits earns participants bonus draws upon completion of the study. Failure to attend a visit without prior approval or failure to complete all visit requirements results in no draws for that visit. The lottery jar contains 500 chips: 250 say “good job,” 219 have a value of \$1, 30 have a value of \$5, and 1 has a value of \$100. The study completion bonus will be 5 extra draws. Thus, at each visit, subjects will have the opportunity to make 5 draws from the lottery jar, for maximum possible earnings of \$120 per visit.

Participants will be paid in cash for intake visits. At the baseline visit participants will be issued a Greenphire ClinCard, which is a reloadable, pre-paid card for the purposes of compensation. Compensation will be loaded onto the ClinCard at the end of successfully completed visits. Participants may opt to receive a text message alert when a payment has been loaded onto the ClinCard.

TRAVELING VIA THE RIDE SERVICE

Participants may elect to use “Roundtrip”, which is a ride service that partners with Lyft to coordinate roundtrip rides to appointments. Study staff will schedule each ride by using the participant’s first and last name, and phone number via Roundtrip’s HIPAA compliant platform. Participants will receive a reminder 24-48 hours prior to their appointment to confirm their appointment. Participants will receive a second reminder call to notify them of their pickup time, and to confirm important details pertaining to their round-trip ride. If the study staff cannot reach the participant by 5pm the day prior to their appointment, their ride may be cancelled. If the participant confirms their appointment after 5pm the day prior to their appointment, they will still be permitted to attend the visit and will receive \$10 to cover their travel expenses if they attend. If a participant needs to cancel a previously confirmed ride, they must do so by contacting the study staff directly, preferably by 5pm the day prior to their appointment. Participants who fail to notify the study staff within this timeframe may no longer be permitted to utilize the ride service at future study visits

Table 3. Study Compensation

Time Point	Study Week	Session Length	Visit Compensation	Quit Incentives ²	Completion Bonus	Total Estimated ⁶	Travel Reimbursement ⁵	Lottery Jar ⁷
Intake	0	~3hrs	\$10	N/A	N/A	\$10	\$10	5 draws
Scan 1	1	~4hrs	\$90	N/A	N/A	\$90	\$10	5 draws
Scan 2	2	~4hrs	\$90	N/A	N/A	\$90	\$10	5 draws
Back-up Scan ¹	1	~45min	\$15	N/A	N/A	(\$15 ¹)	\$10	5 draws

Pre-Quit Visit	3	~1.5hrs	\$20	N/A	\$70 ²	\$90	\$10	5 draws
Target Quit Date	4	~45min	\$20	N/A	N/A	\$20	\$10	5 draws
Monitoring Visit 1	5	~45min	\$10	\$35 ³	N/A	\$45	\$10	5 draws
Monitoring Visit 2	5	~45min	\$10	\$40 ³	N/A	\$50	\$10	5 draws
Monitoring Visit 3	6	~45min	\$10	\$75 ³	N/A	\$85	\$10	5 draws
Monitoring Visit 4	7	~45min	\$10	\$75 ³	N/A	\$85	\$10	5 draws
Monitoring Visit 5	8	~45min	\$10	\$75 ³	\$50 ⁴	\$135	\$10	Up to 10 draws
6-Month Follow-up Phone Call	28	~15min	\$35	N/A	N/A	\$35	N/A	
Abstinence Verification	28	~30min	\$35	N/A	N/A	\$35	\$10	
12-Month Follow-up Phone call	52	~15min	\$25	N/A	N/A	\$25	N/A	
TOTALS			\$390	\$300	\$120	\$810	\$120	

¹ Some participants may be double booked for visits including an fMRI. This will ensure that valuable time on the scanner is not wasted. Participants that are booked as back up participants will be fully aware of their status as the backup and will have agreed to be available in the event that the primary participant does not attend the visit. If the participant is not needed for a scan on the day that they are signed up as a backup, they will earn \$25 for their time and availability- and will be scheduled as a primary candidate for the next available scanning session.

² Participants who complete both fMRI scan visits will receive a \$70 bonus at their Pre-Quit visit.

³ In order to receive quit incentives participants must have a CO less than or equal to 5PPM at all monitoring visits and/or a NicAlert value of less than or equal to level 2 (non-user of tobacco products) MV2-MV5, depending on prior monitoring visit quit status.

⁴ To earn this bonus, participants must have achieved at least 4 out of 5 monitoring visits.

⁴ Participants who attend at least 4 out of 5 monitoring visits will receive a \$50 completion bonus at their Monitoring Visit 5.

⁵ Only applicable to participants who opt to receive \$10 travel reimbursement for that visit.

⁶ Maximum total compensation estimated if participant opts to utilize ride service for transportation coverage. If a participant is deemed ineligible during a study visit, they will only receive \$10 for their time in addition to their preferred travel coverage.

⁷ Participants will be given 5 draws from our lottery jar for the chance to earn additional monetary incentives. As a bonus for completing the study, participants will get an additional 5 draws from the lottery jar during their final visit.

INFORMED CONSENT

1. Consent Process

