Functional magnetic resonance imaging (fMRI) studies by our team converge on the central role of working memory in smoking relapse. We showed that brief (e.g., 24 hr.) abstinence from smoking produces working memory deficits that are associated with reduced neural activity in cognitive control circuits and weakened resting state functional connectivity [25-29]. These altered brain responses may compromise cognitive resources needed to resist urges to smoke, thereby contributing to relapse [26, 30]. While working memory is one mechanism underlying relapse, additional neurobehavioral pathways are clearly important [31]. For example, neural reactivity to smoking cues also increases risk of relapse [31, 32]. Further, psychological stress can enhance neural responses to smoking cues [33, 34] and increase smoking intensity [35, 36]. Stress can also impair working memory [37]. The proposed study, to our knowledge, will be the first prospective study to examine the contributions of resting BOLD and BOLD signal change during working memory, cue reactivity, and psychological stress to subsequent smoking relapse. We will determine whether these mechanisms contribute to relapse beyond subjective and behavioral assessments, and explore the interactions among these processes.

Using our validated fMRI abstinence challenge paradigm [25, 27-30], 200 smokers will complete two 1-hour pre-treatment fMRI scans: after smoking satiety and after 24 hours of confirmed abstinence. We will examine neural responses during performance of tasks probing working memory, cue reactivity, and stress response as well as resting state functional connectivity. Participants will then set a target quit date, receive smoking cessation counseling, and be monitored for 6 months to assess time (days) to relapse, using a validated smoking relapse protocol [30, 38]. The primary outcome is time to relapse. Secondary outcomes include abstinence symptoms and smoking status at 30 days.

OBJECTIVES

1. Overall Objectives - (Main Study)

Aim 1: To identify brain mechanisms that increase vulnerability to relapse, using a pre-treatment abstinence challenge paradigm.

Hypothesis: *Altered Blood Oxygen Level Dependent (BOLD) signal during 24-hr abstinence challenge (vs. smoking satiety) will increase the risk of faster relapse during a subsequent quit attempt.*

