Aim 2: To test an integrated brain-behavior model of relapse. *Hypothesis: Integration of neural and behavioral predictors will identify novel spatial patterns that distinguish quitters from relapsers at 30 days.*

BACKGROUND – Recruitment & Retention Pilot Study

Nearly one in three clinical trials closely prematurely due to under-enrollment [67]. Reports of clinical trials consistently state that initial approaches to recruitment are rarely successful, take longer and are more costly than planned, and the pool of participants is overestimated [68]. Unfortunately, many studies implement recruitment strategies without taking a systematic approach to identifying the most efficient and cost-effective approaches to enrolling subjects. With the increasing ubiquity of cell phones, text messaging (SMS) interventions have the potential to increase reach and reduce costs. In the United States, it is estimated that 85 to 91% of adults (18 and over) own a mobile phone, and these rates are observed across low- and high-income individuals [69]. SMS interventions for improving adherence to antiretroviral treatment in people living with HIV as well as smoking cessation have demonstrated efficacy [70]. However, few studies have explicitly examined strategies to optimize the use of SMS to enhance clinical trial enrollment. Behavioral economic strategies, including information provision and incentives, may represent useful approaches to overcoming barriers to clinical research and ultimately advancing science [71]. Information provision includes utilizing descriptive and injunctive norms, personalization, and reciprocity. Framing messages to shape social norms regarding research participation may increase engagement. For example, in addition to “personal medical benefit”, patients cite “contributing to research that could help other people” and “giving something back in return” as the most important reasons to participate in clinical research [72]. Another common strategy for improving recruitment and retention is to offer incentives, including monetary payments or other rewards that target motivation. For instance, contingency management (CM), where tangible reinforcement is provided in close temporal proximity to a participant performing a target behavior (e.g., on-time attendance) is highly efficacious in engendering target behaviors [73-75]. Although information provision and incentives are effective strategies for behavior change, they may target different aspects of motivation: intrinsic (i.e., the behavior itself is purposive) vs. extrinsic motivation (i.e., the prospect of gaining the incentive motivates the behavior), respectively. Although numerous studies comparing intrinsic vs extrinsic strategies to enhance motivation have yielded inconsistent results, a recent meta-analysis suggested intrinsic and extrinsic factors may act synergistically [76]. Thus, we propose to employ information provision and incentive strategies independently and in combination to evaluate the optimal approach for recruiting and retaining subjects in clinical research studies.

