N-back task, analysis will focus on the parametric effect of increasing working memory load across four levels (linearly modeled [-3 -1 1 3]). For the cue reactivity task, the primary contrast will be smoking cues>neutral cues. For the stress task, the primary contrast will be stress > control blocks.

Subject-level statistical image maps will be transformed into a common anatomic space (Montreal Neurological Institute, MNI) for group-level analysis. Session (abstinence vs. smoking) whole brain, voxelwise analyses will test abstinence effects in brain regions specified above. The peak voxel in each significant cluster will be used to assign appropriate anatomical labels. Percent signal change within significant clusters will be utilized in regression models described below. Age, self-reported ethnicity, nicotine dependence severity (FTND), and withdrawal symptom severity will be included as covariates in the relevant statistical models. For all tests, significance will be determined using cluster $p < .05$ and voxel-height $Z > 2.33$.

Aim 1: Modeling of Days to Relapse:

The outcome associated with Aim 1 is censored time to event and the predictors are continuous measures (difference scores) extracted from ROIs associated with each neurobehavioral domain. We will test this hypothesis within each domain (working memory, cue reactivity, and stress) using Cox regression; the test statistic will be the z-score corresponding to the hazard ratio, with significance corrected for the total (8) cross domain ROIs. We will also test baseline clinical predictors and abstinence challenge-related performance measures (difference scores) for entry into each of the domain specific models.

Aim 2: Integrated Brain-Behavior Model:

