We anticipate that abstinence-induced deficits in working memory in the Left DLPFC will predict time to relapse, as will brain responses to cues and to stress. We predict that the effect of brain responses to cues (two regions) and to stress (three regions) on days to relapse is moderated by abstinence-induced deficits in left DLPFC activity. Provided that left DLPFC deficit shows some importance in Aim 1 ($p < 0.2$), we will enter the main effect into the cue and the stress models of relapse. Further, we will test interactions of left DLPFC working memory deficit with ROIs in the cue and stress models that have also shown promise in Aim 1 ($p < 0.2$). Interactions will be tested at $\alpha = 0.05$ using the z-score corresponding to the ratio of hazard ratios (HRR).

Power and Sample Size Considerations:

Power analyses were conducted using PASS v 13.0 (Power and Sample Size, NCSS, Kaysville, UT). For Aim 1 we considered three neurobehavioral domains containing a total of 8 ROIs (predictors). We expect that predictors will be correlated, and therefore pure Bonferroni correction is too conservative [66]. In our preliminary data, within domain (e.g. working memory) correlation falls between 0.5 and 0.6 but between domains (e.g. working memory, cue reactivity) the correlation is weaker. Accounting for this weak inter-correlation, we will set alpha at $p < 0.0085$. A sample of 200 participants provides 80% power to detect a one-sample effect size of 0.25, or a hazard ratio of 1.32. Effect sizes (Cohen's d for a one-sample test) observed in our prior study [30] ranged from 0.245-0.297.

Recruitment & Retention Pilot Study:

Power is provided for our primary aim. The analysis will compare the enrollment rates between the four intervention arms, and examine main and interaction effects. For SR arm, we expect a 28% of subjects who schedule an Intake will be eligible and enroll (based on existing data across the four studies). With the proposed sample of 576, we have >80% power ($\alpha = .05$) to detect a difference between the SR arm and the IP and CM arms of 12%, corresponding to an OR of 1.75. For the interaction term, we have 80% power ($\alpha = .05$) to detect a departure from additivity of the main effects corresponding to a ratio of odds ratios (ORR) of 5.5.

3. Confidentiality

Confidentiality of the data generated in this study shall be maintained in the following ways:

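### The Aim 2 hypothesis about spatial patterns and 30-day quitter status has no matching analysis; the analysis headed Aim 2 tests moderation of days to relapse

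*Combined protocol and SAP*

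**What the plan says.** Objectives, Overall Objectives (Main Study), gives Aim 2 as a test of an integrated brain-behavior model of relapse. Its hypothesis is: "Integration of neural and behavioral predictors will identify novel spatial patterns that distinguish quitters from relapsers at 30 days".

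Statistical Analysis, Aim 2: Integrated Brain-Behavior Model, makes a different prediction: "We predict that the effect of brain responses to cues (two regions) and to stress (three regions) on days to relapse is moderated" by the left DLPFC deficit. Entry is conditional: "Provided that left DLPFC deficit shows some importance in Aim 1", with p<0.2 as the threshold. Interactions are then tested only for cue and stress regions that also reached p<0.2 in Aim 1. Each is tested at alpha 0.05 with the z-score for a ratio of hazard ratios (HRR).

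Four other places bear on the point:

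- Task fMRI, group level: "Session (abstinence vs. smoking) whole brain, voxelwise analyses will test abstinence effects in brain regions specified above". Percent signal change in the significant clusters then goes into the regression models. Age, self-reported ethnicity, "nicotine dependence severity (FTND), and withdrawal symptom severity will be included as covariates in the relevant statistical models".
- Aim 1, Modeling of Days to Relapse: "We will also test baseline clinical predictors and abstinence challenge-related performance measures (difference scores) for entry into each of the domain specific models".
- Background (Main Study): "Secondary outcomes include abstinence symptoms and smoking status at 30 days".
- Measures, Primary Outcomes (Main Study): 7-day and 30-day point prevalence are secondary outcomes, and drop-outs count as relapsers.

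**The concern.** A hypothesis and the analysis under the same aim number should share an outcome, a set of predictors and a criterion for success. Here they share none of the three in full. The team could follow the plan exactly and still have no result on the question it set for Aim 2.

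There are two practical risks. First, the HRR result may be reported as the answer to Aim 2. A null interaction could then be read as failure to tell 30-day quitters from relapsers, although main effects alone could separate the groups. A positive interaction could be read as support for spatial patterns that nobody examined. Second, any 30-day analysis added later would be unplanned in its predictors, its definition of a quitter and its validation.

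**Working it through.** **The plan's own figure.** The only main-study power statement is for Aim 1: 200 participants, alpha 0.0085, 80% power, effect size 0.25 or hazard ratio 1.32. Two-sided, z = 2.632 for alpha and 0.842 for power.

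- One-sample test: N = ((2.632 + 0.842)/0.25)² = 193. At N = 200 the noncentral-t power is 80.9%, so the stated figure reproduces.
- Cox model, HR 1.32 per SD: events = ((2.632 + 0.842)/ln 1.32)² = 156.5, about 78% of 200. The plan gives no event rate, so this is an implied value.

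Nothing here is in dispute. There is no main-study power statement for Aim 2 to check.

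**Hypothesis and analysis side by side.**

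| | Objectives, Aim 2 hypothesis | Statistical Analysis, Aim 2 |
|---|---|---|
| Outcome | Quitter or relapser at 30 days | Days to relapse |
| Predictors | Neural and behavioral, integrated | Left DLPFC with two cue and three stress regions; no behavioral measure named |
| Criterion | Spatial patterns that separate the groups | Interaction HRR, up to 2 + 3 = 5 tests |
| Condition | None | p<0.2 in Aim 1 for left DLPFC and for the region |

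**Does another part of the plan fill the gap?**

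- The voxelwise analysis is the only spatial one. It contrasts abstinence with smoking in the same people. Its clusters supply predictors for the relapse regressions, but no map or pattern is compared between quitters and relapsers.
- Behavioral and clinical measures can enter the Aim 1 domain models, and FTND and withdrawal severity are covariates. The only outcome named for these models is days to relapse.
- Smoking status at 30 days and 30-day point prevalence are named as outcomes. No model is given for either.

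None of these tests the stated hypothesis.

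**How often would the p<0.2 condition stop Aim 2?** For a standardised predictor with D events, the chance of two-sided p<0.2 is about Φ(√D × ln HR − 1.282) + Φ(−√D × ln HR − 1.282). The event counts and the hazard ratios other than 1.32 are assumptions.

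| True left DLPFC hazard ratio | Events | Chance of missing p<0.2 |
|---|---|---|
| 1.32 | 100 | 7% |
| 1.32 | 120 | 4% |
| 1.32 | 156.5 | 1% |
| 1.32 | 200 | 0.4% |
| 1.15 | 156.5 | 32% |
| 1.00 | any | 80% |

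For example, at HR 1.32 and 156.5 events, √156.5 × 0.2776 = 3.473. Then Φ(3.473 − 1.282) = 0.986, so the miss rate is about 1%. The condition is a minor obstacle at the design effect. It matters mainly when left DLPFC has little main effect, and a moderator can be in exactly that position.

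**The case against.** The strongest reply is that Aim 2, broadly worded, asks for an integrated brain-behavior model of relapse, and the Cox models go some way towards that. The cue and stress models may already carry behavioral and clinical covariates. Spatially derived cluster signal feeds the regressions. The HRR tests match the moderation prediction made in the analysis section itself. All of this stands. It means that the plan is coherent within its analysis section and that the gap lies between that section and the Objectives.

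It may also be said that a real interaction implies some separation of the groups at 30 days. That is true, but it is indirect evidence. The HRR does not measure the separation, and its absence does not rule separation out. If spatial patterns is taken to mean no more than the chosen regions, a 30-day comparison of quitters with relapsers is still missing.

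A reader might infer that the p<0.2 condition will usually block Aim 2. At HR 1.32 it will not. The prediction that left DLPFC, cue and stress responses each relate to time to relapse is tested in Aim 1 in any case.

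**Conclusion.** The point holds as a mismatch between a stated hypothesis and its analysis. The hypothesis concerns 30-day status, integrated predictors and spatial patterns. The analysis concerns moderation of days to relapse. Neither a positive nor a null HRR can confirm or refute the hypothesis as written, and no fallback analysis exists if left DLPFC misses p<0.2.

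A reader might go further and infer that the main study is compromised. The documents do not support that. Days to relapse remains the primary outcome, Aim 1 has a matching Cox analysis, and its stated power reproduces.

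The conclusion rests on the text and needs no numerical assumption. Only the miss rates do: a standardised predictor, the normal approximation and assumed event counts. The public file has a gap between the informed-consent heading and the staff list, which I assume holds no analysis. The correction should be made, and it is cheap.

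**What to change.** Choose one.

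**A. Restate the aim and hypothesis in Objectives as the question analysed.** For example: the abstinence-induced left DLPFC deficit moderates the effects of cue and stress responses on days to relapse, in models that may include the planned behavioral and clinical covariates. Draw no conclusion about spatial patterns or 30-day discrimination. This costs a short text change and gives up that claim.

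**B. Keep the hypothesis and add one prespecified analysis of 30-day quitter or relapser status, not conditional on Aim 1.**

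- Derive status from the relapse definition under Measures, Primary Outcomes (Main Study), with drop-outs as relapsers.
- Use the planned region and cluster signal-change scores plus the behavioral measures already collected.
- Compare with a behavior-only model by cross-validation, with all feature selection inside the folds.
- Name a multivariate spatial-pattern method, or remove the claim of novel spatial patterns.

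This costs extra analysis but no new visit. Precision is limited with 200 participants. The gain should be judged by the paired difference in AUC between the two models, because the confidence interval of a single AUC does not describe that comparison.

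Under either option, report the HRR tests as moderation results only.
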